8.2 Sample Size Derivation

8.2.1 Safety Lead-in Sample Size

The Safety lead-in is not formally powered to assess any statistical hypotheses. In this part, 12 to 20 eligible patients (6-12 from US, 6-8 from ROW) will be enrolled to receive varlitinib plus capecitabine.

Patients in this group will be replaced if study medication compliance is < 85% in the first 14 days.

8.2.2 Part 1 Sample Size

Part 1 is designed with co-primary endpoints ORR and PFS. In order to maintain an overall, 1-sided 10% type I error rate for Part 1, a Hochberg procedure¹⁵ will be used, such that the study will be deemed to have met its primary objective if either endpoint is significant at the 1-sided 5% level or if both endpoints are significant at the 1-sided 10% significance level.

One hundred and twenty patients provide approximately 80% power to detect a true difference of 17% in response rate, based on a 1-sided 5% significance level and assuming 10% response rate for the placebo group and a 27% response rate for varlitinib. To ensure the adequate data are available to evaluate the effects of varlitinib on both co-primary endpoints, the DCO for the primary analysis will be the later of 3 months after last patient in and when 70% of patients (84 patients) have experienced a PFS event. Based on a minimum of 84 PFS events at the time of the primary analysis, the study would have a minimum of 80% power to detect a true HR of 0.58 for PFS based on a 1-sided 5% significance level.

Furthermore, if the primary objective of the study is met, the following approach to type I error control will be applied in order to support marketing approval:

- The overall type I error rate for marketing approval will be controlled at the two-sided 5% level, using a Hochberg procedure
- Using this approach, statistical significance may be claimed if *either* ORR or PFS is significant at the two-sided 2.5% significance level or if *both* ORR and PFS are significant at the two-sided 5% significance level.

One hundred and twenty patients provide approximately 80% power to detect a true difference of 20% in response rate, based on a 2-sided 5% significance level and assuming 10% response rate for the placebo group and a 30% response rate for varlitinib.

A total of 84 PFS events provides 80% power to detect a true HR of 0.54, based on a two-sided 5% significance level. Assuming a 8-month non-linear recruitment period, a 2.67 month median PFS for capecitabine alone, and a true HR of 0.54, it is estimated that the DCO for the primary analysis of Part 1 will occur approximately 12 months after the first patient is randomized into the study (first patient in).

Overall Survival is a secondary endpoint in Part 1. A preliminary analysis of OS will be performed at the time of the primary analysis of ORR and PFS. It is anticipated that the OS data at this time will be immature, thus a second analysis of OS is planned for when approximately 95 patients (approx. 79%) have an OS event. Due to the number of OS events expected at the time of the first analysis, this initial analysis of OS will be considered exploratory only. Although a p-value may be presented, for the purpose of marketing authorization, no claims of statistical significance will be based on the initial analysis. For the purpose of type I error control across the two analyses of OS in support of marketing authorization, the OS update analysis will be considered the primary analysis of OS for Part 1 of the study, and statistical significance will be assessed at the two-sided 5% significance level.

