Sample Size:	
Part 1:
 
The study is designed with co-primary endpoints, ORR, and PFS. In order to maintain an overall 1-sided 10% type I error rate for the study, a Hochberg procedure will be used, such that the trial will be deemed to have met its primary objective if either endpoint is significant at the 1-sided 5% level or if both endpoints are significant at the 1-sided 10% significance level.
 
To ensure that adequate data are available to evaluate the effects of varlitinib on both co-primary endpoints, the DCO for the primary analysis will be the later of 3 months after the last patient in or when 70% of the patients (84 patients) have experienced a PFS event. Based on a minimum of 84 PFS events at the time of the primary analysis, the study would have a minimum of 80% power to detect a true Hazard Ratio (HR) of 0.58 for PFS, based on a 1-sided 5% significance level.
 
Furthermore, if the primary objective of the study is met, the following approach to type I error control will be applied in order to support marketing approval:
 
 • The overall type I error rate for marketing approval will be controlled at the two-sided 5% level, using a Hochberg procedure • Using this approach, statistical significance may be claimed if either ORR or PFS is significant at the two-sided 2.5% significance level or if both ORR and PFS are significant at the two-sided 5% significance level. 
One hundred and twenty patients will provide approximately 80% power to detect a true difference of 20% in response rate, based on a 2-sided 5% significance level and assuming a 10% response rate for the placebo/capecitabine group and a 30% response rate for the varlitinib/capecitabine group.
 
A total of 84 PFS events provides 80% power to detect a true HR of 0.54, based on a two-sided 5% significance level. Assuming an 8-month non-linear recruitment period, a 2.67-month median PFS for capecitabine alone, and a true HR of 0.54, it is estimated that the DCO for the primary analysis of Part 1 will occur approximately 12 months after the first patient is randomized into the study (first patient in).
 
Part 2:
 
Part 2 is designed with a primary endpoint of OS. Approximately 350 patients will be randomized (1:1) to obtain 247 OS events. If the true OS HR for the comparison of varlitinib + capecitabine vs. placebo + capecitabine is 0.7, the study will have approximately 80% power to demonstrate a statistically significant difference for varlitinib, based on a 2-sided 5% significance level.
 
Assuming a 24-month non-linear recruitment period whereby the proportion of patients recruited by the end of the month i is $(i/24)^2$, a median OS of 6 months for

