This study will commence initially with a Safety lead-in group designed as a single arm, open label study to assess the safety of varlitinib plus capecitabine in a small set of patients (12 to 20) prior to commencing Part 1 in a larger study population (n=120). A DSMB will review safety data on 2 occasions (refer to [Section 7.2](#)) to monitor the safety of patients. Part 2 (n=350) of the study will not commence until the results of Part 1 have been evaluated.

Part 1 of the study includes co-primary endpoints of ORR and PFS determined via central review. Overall survival is the primary endpoint in Part 2 of the study. These are well known endpoints for oncology studies and have been used to support health authority decisions on drug approvability.

In Part 1 of the study, for the purpose of marketing approval, a Hochberg procedure will be used to control the overall type I error rate associated with the co-primary endpoints, ORR and PFS, at the two-sided 5% level. Using this approach, statistical significance can be declared if *either* ORR or PFS is significant at the two-sided 2.5% level, or if *both* endpoints are significant at the two-sided 5% significance level. For significance at the 2-sided 5% level, the study has approximately 80% power to detect a 20% difference in ORR, assuming a 10% response rate for the control arm. Similarly, for significance at the two-sided 5% level, 84 PFS events would provide approximately 80% power to detect a true HR of 0.54 (approximately an 84% prolongation in PFS). If statistical significance is demonstrated, ASLAN believes that these effect sizes represent a clinically meaningful improvement in efficacy relative to the current care options. This improvement would represent a step-change in the treatment options for patients with second line BTC. To enable a further illustration of the clinical benefit realized through the improvement in ORR, DoR will be included as a secondary endpoint in the study and will help characterize the durability of the observed responses. All radiological data collected in

the Part 1 of the study will be assessed via an ICR of the imaging data thus eliminating the potential bias that can arise from site evaluations.

Data from the Safety lead-in, Part 1 and Part 2 will be evaluated separately for safety and efficacy. Patients whose data contributed to the Part 1 analysis will not be included in the Part 2 analysis.

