8.5 Methods of Statistical Analysis

8.5.1 Primary Endpoints

8.5.1.1 Part 1 - Objective Response Rate

The primary analysis will test for the superiority of varlitinib-containing treatment arm relative to the placebo-containing arm.

Objective response rate will be analyzed using a stratified exact binomial test^{16,17} that extends Fisher's Exact test to more than one stratum. The analysis will be stratified by

primary tumor location (gallbladder/NonGB). The 2-sided p-value will be obtained by doubling the 1-sided p-value.

The conditional maximum likelihood estimate of the odds ratio will be presented together with its exact 2-sided 95% confidence limit, which excludes one if and only if the stratified exact binomial test is significant at a 2-sided 5% level. Corresponding significance levels and confidence intervals (CIs) will be calculated using tests performed at a 1-sided 10% level. The 1-sided p-value will also be presented.

To test for heterogeneity across strata, the exact test of Zelen¹⁸ will be performed testing whether the treatment effect differs between the 2 strata included in the primary analysis.

For Part 1 only, subgroup analyses will be conducted comparing ORR between treatments in the subgroups of the FAS set defined by the stratification factors declared at randomization, Region (US/Non-US) and primary tumor location (GB/Non-GB), plus the following factors:

- Gender (male vs female)
- Race (Asian/Caucasian/Other)
- Baseline ECOG status (0/1)
- Extent of disease (locally advanced/metastatic)
- Age (<60/>=60)
- Baseline HER2 expression (positive defined as +++ or above by IHC, otherwise negative)
- Any HER positivity (positive defined as + or higher by IHC for HER1, HER2, HER3, HER4, or otherwise negative)

Note: The sub-group analyses based on IHC biomarker data will be reported outside of the main CSR.

Other baseline variables may also be included if there is clinical justification or an imbalance is observed across the treatment arms. For each sub-group, the odds ratio and corresponding 80% CI will be presented on a forest plot including the odds ratio and 80% CI from the overall population. Additionally, if the primary analysis of ORR is significant at the 2-sided 5% level in the overall population, the forest plot will be replicated using 95% CI.

No adjustment to the significance level for testing will be made since all these analyses will be considered supportive of the primary analysis of ORR.

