### 6.1 Sample Size Estimation

#### 6.1.1 Safety Lead-in

The Safety lead-in is not formally powered to assess any statistical hypotheses. In this part, 12 to 20 eligible subjects (with at least 6 from the US) will be enrolled to receive varlitinib plus capecitabine.

Subjects in this group will be replaced if varlitinib compliance is < 85% in the first 14 days.

#### 6.1.2 Part 1

Part 1 is designed with co-primary endpoints, ORR and PFS. In order to maintain an overall, one-sided 10% type I error rate for Part 1, a **Hochberg** procedure will be used, such that the trial will be deemed to have met its primary objective if either endpoint is significant at the one-sided 5% level, or if both endpoints are significant at the one-sided 10% significance level.

One hundred and twenty subjects provides approximately 80% power to detect a true difference of 17% in response rate, based on a one-sided 5% significance level and assuming 10% response rate for the placebo group and a 27% response rate for varlitinib. To ensure the adequate data are available to evaluate the effects of varlitinib on both co-primary endpoints, the data cut-off for the primary analysis will be the later of 3 months after LSI, and when 70% of subjects (84 subjects) have experienced a PFS event. Based on a minimum of 84 PFS events at the time of the primary analysis,

the trial would have a minimum of 80% power to detect a true HR of 0.58 for PFS, based on a one-sided 5% significance level.

Furthermore, if the primary objective of the study is met, the following approach for type I error control will be applied in order to support marketing approval:

- The overall type I error rate for marketing approval will be controlled at the two-sided 5% level, using a Hochberg procedure
- Using this approach, statistical significance may be claimed if *either* ORR or PFS is significant at the two-sided 2.5% significance level or if *both* ORR and PFS are significant at the two-sided 5% significance level.

One hundred and twenty subjects provides approximately 80% power to detect a true difference of 20% in response rate, based on a two-sided 5% significance level and assuming 10% response rate for the placebo group and a 30% response rate for varlitinib.

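### The stated power of about 80% for ORR belongs to a large-sample test; the exact test the plan specifies has about 72% and 73%.

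*Protocol*

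**What the plan says.** Part 1 randomises 120 patients, 60 per arm (protocol 5.3.1). Protocol 8.2.2 gives two power statements for ORR:

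- "One hundred and twenty patients provide approximately 80% power to detect a true difference of 17% in response rate", for 27% versus 10% at one-sided 5%.
- "One hundred and twenty patients provide approximately 80% power to detect a true difference of 20% in response rate", for 30% versus 10% at two-sided 5%.

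SAP 6.1.2 repeats both ("One hundred and twenty subjects provides approximately 80% power to detect a true difference of 17% in response rate" and "One hundred and twenty subjects provides approximately 80% power to detect a true difference of 20% in response rate"). The 20-point claim is also in the synopsis ("One hundred and twenty patients will provide approximately 80% power to detect a true difference of 20% in response rate") and in protocol 5.2 ("the study has approximately 80% power to detect a 20% difference in ORR"). None of these places names the test behind the figure.

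The analysis sections do name a test. Protocol 8.5.1.1 says "Objective response rate will be analyzed using a stratified exact binomial test", describes it as extending Fisher's exact test to several strata, and adds: "The 2-sided p-value will be obtained by doubling the 1-sided p-value". SAP 7.1 specifies the same test and the same doubling rule. The protocol stratifies by tumour location (2 strata); the SAP stratifies by region and tumour location (4 strata) and allows region to be dropped.

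**The concern.** Fisher-type exact tests are conservative when responders are few, because the attainable p-values are coarse and the test cannot spend its full nominal alpha. With 60 per arm and control response at 10%, the loss of power against a large-sample test can be material. A round 80% that names no test therefore needed checking against the test that will be run.

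ORR is one of two co-primary endpoints and is intended to support marketing approval. Protocol 5.2 rests its design argument partly on about 80% power for a 20-point difference. If the true figure is lower, a non-significant ORR result would be judged against a sensitivity that the ORR test does not have at the stated level.

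**Working it through.** **Inputs.** 60 patients per arm (protocol 5.3.1), with no dropout allowance because the analysis set is all randomised patients (protocol 8.3.2).
- Scenario A: 10% versus 27%, one-sided 5%.
- Scenario B: 10% versus 30%, two-sided 5%. Under the doubling rule this means one-sided exact p ≤ 0.025.

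**Step 1: reproduce the plan's figure.** Let X_c ~ Bin(60, p_c) and X_t ~ Bin(60, p_t) be the responder counts. The uncorrected statistic is Z = (X_t − X_c)/60 ÷ √[2·p̄(1 − p̄)/60], with p̄ = (X_t + X_c)/120. Power is the total binomial probability of all outcomes with Z ≥ 1.645 (A) or Z ≥ 1.960 (B).

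| Method | A: 27% v 10% | B: 30% v 10% |
|---|---|---|
| Chi-square, enumerated | 79.1% | 80.2% |
| Unpooled normal formula | 79.2% | 80.7% |
| Arcsine formula | 79.3% | 80.6% |
| Pooled normal formula | 78.0% | 78.9% |

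The stated figures are thus a correct large-sample calculation.

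**Step 2: the specified test.** Given s = X_c + X_t responders in total, the one-sided p-value is P(H ≥ X_t), where H is hypergeometric (population 120, 60 on varlitinib, s drawn). Power is Σ Bin(x_c; 60, p_c)·Bin(x_t; 60, p_t) over all 61 × 61 outcomes with p ≤ 0.05 (A) or p ≤ 0.025 (B).

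| | A | B |
|---|---|---|
| Exact power | 72.4% | 73.0% |
| Shortfall from chi-square | 79.1 − 72.4 = 6.7 points | 80.2 − 73.0 = 7.2 points |
| Shortfall from 80% | 7.6 points | 7.0 points |

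**Step 3: why they differ.** Take 6 of 60 responders on control.
- At one-sided 5%, 13 responders on varlitinib suffice for chi-square (p = 0.040) but not for the exact test (p = 0.066). The exact test needs 14 (p = 0.042).
- At one-sided 2.5%, 15 suffice for chi-square (p = 0.015) but not for the exact test (p = 0.026). The exact test needs 16 (p = 0.016).

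When both arms respond at 10%, the exact test rejects 2.8% of the time at nominal 5% and 1.1% at nominal 2.5%. Chi-square rejects 5.1% and 2.5%.

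**Step 4: stratification.** The stratified conditional test was simulated with response rates common across strata and with assumed stratum sizes.
- Two strata, 30%, 40% or 50% gallbladder: 73.3%, 72.3%, 72.3% (A) and 73.4%, 73.0%, 72.9% (B).
- Four strata, 20% US (the share in protocol 5.2), 30% or 50% gallbladder: 71.5%, 72.9% (A) and 73.1%, 73.1% (B).

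With 20,000 runs the simulation error is about 0.3 points, so the result is the same under the protocol's and the SAP's stratification.

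**Step 5: what 80% would take.**
- Patients at the stated rates: 73 per arm in A (146 in total, power 80.3%) and 69 per arm in B (138 in total, 80.7%).
- Varlitinib response rate at 120 patients: 29.0% in A (19 points) and 31.9% in B (about 22 points).

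**Step 6: PFS for comparison.** Power = Φ(|ln HR|·√84/2 − z).
- HR 0.58, one-sided 5%: 0.5447 × 4.583 − 1.645 = 0.851, giving 80.3%.
- HR 0.54, two-sided 5%: 0.6162 × 4.583 − 1.960 = 0.864, giving 80.6%.

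Both match the plan.

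**Step 7: the Hochberg rule.** Assume that both planned effects are true and that the endpoints are independent.
- *Primary objective.* ORR power is 72.4% at one-sided 5% and 82.2% at 10%; PFS power is 80.3% and 88.8%. At least one endpoint succeeds: 1 − 0.276 × 0.197 + (0.822 − 0.724)(0.888 − 0.803) ≈ 0.954. ORR is claimed: 0.724 + (0.822 − 0.724) × 0.888 ≈ 0.811.
- *Marketing.* ORR power is 63.1% at two-sided 2.5% and 73.0% at 5%; PFS power is 72.0% and 80.6%. At least one endpoint succeeds: 1 − 0.369 × 0.280 + (0.730 − 0.631)(0.806 − 0.720) ≈ 0.905. ORR is claimed: 0.631 + (0.730 − 0.631) × 0.806 ≈ 0.711.

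**The case against.** The strongest reply has three parts.

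First, the plan says approximately, names no test for its power figures, and uses an ordinary planning formula correctly. This is a mismatch between planning method and analysis, not a slip in arithmetic. That description is fair, but a gap of 7 to 8 points is more than rounding: it moves the type II error from 20% to about 27%, while the PFS figures in the same section are accurate to within a point. A mid-p version of the conditional test would come closer (77.7% and 79.4%), but neither document specifies mid-p.

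Second, the Hochberg rule lets ORR succeed at a looser level when PFS also succeeds. With both planned effects true and the endpoints independent, ORR is claimed for the primary objective about 81% of the time. This stands and softens the consequence at that level. At the marketing level the corresponding figure is only about 71%. The plan's sentences also give power at a named significance level, not the chance of a claim under Hochberg, so they remain wrong for the named test.

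Third, the practical harm is limited. The exact test errs on the safe side for type I error, and the chance that at least one endpoint succeeds stays high. That is true. It limits the severity but does not make the stated figure correct.

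**Conclusion.** The concern holds. For the test specified in protocol 8.5.1.1 and SAP 7.1, 120 patients give about 72% power for 27% versus 10% at one-sided 5% and about 73% for 30% versus 10% at two-sided 5%, where the plan states about 80% for each.

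The result rests on exactly 60 patients per arm and the response rates given in the plan. The stratified figures also assume response rates common across strata and the stratum sizes listed, because the documents give no rates by stratum.

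The effect is confined to the planning statement for ORR. If both planned effects are true and independent, at least one co-primary endpoint still succeeds about 95% of the time for the primary objective and about 90% for marketing. This should be fixed, but it does not threaten the validity of the trial.

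**What to change.** - In protocol 8.2.2 and SAP 6.1.2, restate the power for 27% versus 10% at one-sided 5% as about 72%.
- In the synopsis, protocol 5.2, protocol 8.2.2 and SAP 6.1.2, restate the power for 30% versus 10% at two-sided 5% as about 73%.
- In each place, say that the figure is computed for the specified exact test. Leave the PFS power statements as they are.

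Optionally, for clarity and not as a correction, add the power under the Hochberg rule. An endpoint that wins alone for marketing is tested at two-sided 2.5%, where power is about 63% for ORR (30% versus 10%) and about 72% for PFS (HR 0.54, 84 events). If these are added, give alongside them the chance of at least one marketing claim (about 90%) and the chance of claiming ORR (about 81% for the primary objective, about 71% for marketing), with the assumptions stated.

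The cost is a less favourable ORR power figure in the text. No patient number, test, threshold or decision rule changes.

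### Marketing-approval power for PFS and ORR is quoted only at two-sided 5%; at the two-sided 2.5% needed to win alone it is about 72% and 63%, and the planned exact ORR test gives 73% even at 5%

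*Protocol*

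**What the plan says.** Protocol section 8.2.2 sets two Hochberg procedures for Part 1.

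- **Primary objective, one-sided 10% overall.** It is met if one endpoint reaches one-sided 5%, or both reach one-sided 10%. Power is given at one-sided 5%: HR 0.58 for PFS, and 10% versus 27% for ORR.
- **Marketing approval, the stricter procedure.** "The overall type I error rate for marketing approval will be controlled at the two-sided 5% level, using a Hochberg procedure". A claim is allowed if either "ORR or PFS is significant at the two-sided 2.5% significance level" or both endpoints reach two-sided 5%.

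For PFS, the marketing power statement is "A total of 84 PFS events provides 80% power to detect a true HR of 0.54"; for ORR it is "One hundred and twenty patients provide approximately 80% power to detect a true difference of 20% in response rate". Both name two-sided 5% as their level. The rates behind the ORR statement are a "10% response rate for the placebo group and a 30% response rate for varlitinib". The synopsis, protocol section 5.2 and SAP section 6.1.2 give the same figures at the same level. None of them gives power at two-sided 2.5%.

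Protocol section 8.5.1.1 analyses ORR with a stratified exact test that extends Fisher's test, and obtains the two-sided p-value by doubling the one-sided one.

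**The concern.** The two procedures are powered on different bases. For the one-sided 10% objective, the quoted level is the one at which an endpoint succeeds without help from the other. For marketing approval, the quoted level is the easier Hochberg step, which counts only when the other endpoint also passes it. Section 5.2 states the Hochberg rule and then gives about 80% per endpoint, so a reader can take 80% as the chance of claiming that endpoint.

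What is at stake is the stated chance of a claim meant to support approval, above all when only one endpoint moves. That case is realistic. SAP section 8 says the change to Hochberg followed reports of durable disease stabilization in a first-line trial, a pattern that could favour PFS without a gain in response rate. The same section says marketing approval previously used hierarchical testing at two-sided 5%. The power text may have been carried over from that rule, but this is an inference.

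**Working it through.** **Inputs.** 84 PFS events, HR 0.54, ORR 10% versus 30%, and the two-sided levels 5% and 2.5% (protocol 8.2.2); 60 patients per arm (5.3.1); exact test with doubled one-sided p (8.5.1.1). Critical values: 1.960 for two-sided 5%, 2.241 for two-sided 2.5%.

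**1. PFS (Schoenfeld).** Power = Φ(√d/2 × |ln HR| − z).
- √84/2 × |ln 0.54| = 4.583 × 0.616 = 2.824.
- Two-sided 5%: Φ(2.824 − 1.960) = Φ(0.864) = **80.6%**. This reproduces the stated 80%.
- Two-sided 2.5%: Φ(2.824 − 2.241) = Φ(0.582) = **72.0%**.
- For scale, 80% power at two-sided 2.5% would need 101 events at HR 0.54, or an HR of 0.51 with 84 events.

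**2. ORR, pooled normal approximation.** Power = Φ[(Δ − z√(2p̄(1−p̄)/n)) / √((p₁(1−p₁)+p₂(1−p₂))/n)], with Δ = 0.20, p̄ = 0.20, n = 60. The two standard errors are 0.0730 and 0.0707.
- Two-sided 5%: (0.20 − 0.1431)/0.0707 = 0.804, power **78.9%**. This reproduces the stated figure of about 80%.
- Two-sided 2.5%: (0.20 − 0.1637)/0.0707 = 0.514, power **69.6%**.

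**3. ORR, planned type of test.** All 61 × 61 possible tables were enumerated for an unstratified Fisher test, with one-sided p at most 0.025 or 0.0125.
- Two-sided 5%: **73.0%**. Two-sided 2.5%: **63.1%**.
- Stratification changes little. Simulating the exact test stratified by tumor location, with an assumed gallbladder share of 20%, 30% or 50%, gives 73.2-73.4% and 63.3-63.6%. Four strata (assumed 20% US, 30% gallbladder) give 73.5% and 63.6%.

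| Endpoint and method | Two-sided 5% | Two-sided 2.5% |
|---|---|---|
| PFS, Schoenfeld | 80.6% | 72.0% |
| ORR, pooled normal | 78.9% | 69.6% |
| ORR, exact | 73.0% | 63.1% |

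**4. Full Hochberg rule, both effects real.** PFS is claimed if its p ≤ 0.025, or if its p lies between 0.025 and 0.05 and ORR has p ≤ 0.05. The ORR claim is symmetric. With independent endpoints and the exact ORR test:
- PFS claim: 0.720 + 0.730 × (0.806 − 0.720) = 78.3%.
- ORR claim: 0.631 + 0.806 × (0.730 − 0.631) = 71.1%.
- At least one: 0.720 + 0.631 − 0.720 × 0.631 + (0.806 − 0.720) × (0.730 − 0.631) = 90.5%.

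The documents give no correlation between the two test statistics, so a range is assumed (bivariate normal):

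| Correlation | ORR method | PFS claim | ORR claim | At least one |
|---|---|---|---|---|
| 0 | exact | 78.3% | 71.1% | 90.5% |
| 0.5 | exact | 77.3% | 70.7% | 83.9% |
| 0.8 | exact | 76.5% | 70.9% | 78.9% |
| 0 | normal | 78.8% | 77.1% | 92.3% |
| 0.5 | normal | 78.0% | 76.4% | 86.0% |
| 0.8 | normal | 77.6% | 76.3% | 81.2% |

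**5. Only one effect real** (independent endpoints). If ORR is null, the PFS claim has 72.1% probability. If PFS is null, the ORR claim has 63.3% (exact).

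The condition that the one-sided 10% objective be met first changes none of this. One-sided 1.25% for one endpoint, or 2.5% for both, already meets it.

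**The case against.** The strongest reply is that every power sentence names its level, and no sentence calls 80% the power of the Hochberg rule. That stands for PFS: 80.6% at two-sided 5% is right as labelled. A reader might infer an arithmetic error in the PFS figure, and the documents do not support that. What is missing is the power at the level that governs a lone win.

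A reader might also infer that the marketing rule as a whole has less than the stated power. That does not follow. If both assumed effects are real, the chance of at least one claim is about 79-92%, mostly above 80%, and the PFS claim loses only a few points (about 76-79%). The 72% describes PFS when it gets no help from ORR.

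A third tempting reading is that Hochberg cuts ORR power from 80% to 63%. That mixes two causes. From 78.9% to 73.0%, about 6 points, comes from the exact test replacing the normal approximation; from 73.0% to 63.1%, about 10 points, comes from the level.

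Finally, 84 events is a floor, because the cut-off is the later of 84 events and 3 months after the last patient enters. At two-sided 2.5%, PFS power would be about 75% with 90 events and 78% with 95. This reply stands, but the plan's own statement also uses 84.

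**Conclusion.** The concern holds as incomplete power reporting for the marketing rule, plus an ORR figure that the planned test does not deliver.

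- **PFS:** correct at two-sided 5%, but about 9 points lower (72.0%) at the win-alone level, at the minimum of 84 events. The chance of missing an effect of HR 0.54 that must win alone is 28%, against 19% at two-sided 5%.
- **ORR:** 63.1% at the win-alone level by the exact test, or 69.6% by the approximation that appears to underlie the stated figure. Even at two-sided 5% the exact test gives 73.0%, not about 80%.

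These figures rest on the plan's own effect sizes, proportional hazards, 60 patients per arm and an unstratified exact test; the stratified simulations agree within about a point. The joint probabilities also depend on the assumed correlation. Type I error control is not in question, and nothing here shows that the sample size must change.

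**What to change.** Keep the sample size, cut-off, testing rule and analyses. In the synopsis, protocol sections 5.2 and 8.2.2, and SAP section 6.1.2, replace the marketing power sentences with:

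- marginal power for PFS at HR 0.54 with the minimum 84 events: 81% at two-sided 5% and 72% at two-sided 2.5%;
- marginal power for ORR at 10% versus 30% with 60 per arm: 73% at two-sided 5% and 63% at two-sided 2.5%, naming the exact test as the method;
- the Hochberg probability of at least one claim if both effects are real, with its correlation assumption: 79-91% with the exact ORR test, for correlations of 0.8 down to 0.

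Avoid wording such as 81% for PFS if ORR is also significant. It reads as conditional power, which equals 81% only if the endpoints are independent. With both effects real and the exact ORR test, the conditional figure is about 85%, 88% and 94% at correlations of 0.3, 0.5 and 0.8.

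The cost is text only, and the stated figures become less favourable.
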